6.2 Blinded Data Review Meeting

The Sponsor will convene a blinded data review meeting (BDRM) after the data has been cleaned and before the study is unblinded.

The BDRM will make decisions that will include, but will not be limited to:

- the determination of whether protocol violations are 'important', or not a protocol violation at all;
- · the allocation of subjects to analysis sets;
- changes required to the SAP.

If required, after the BDRM and prior to database lock, a SAP amendment will be issued.

6.3 General Derivations

This section provides details of general derivations. Derivations specific to the parameter of interest are detailed within the specific SAP section:

Randomized study treatment

Where mentioned in this SAP, "Randomized study treatment" will relate to double-blind study treatment (either tideglusib or placebo). In the case of the SAF, this means the treatment that the subject received rather than the treatment that the subject was randomized to.

The first administration of randomized study medication is defined as the first dose of study medication after the date/time of randomization.

Phase

Phase is defined as a subject's treatment period where:

- Screening Phase: relates to the period ending the day of Visit and dosing commences the next day.
- Run-In Phase: relates to the period starting the day after Visit and ending immediately before the date/time of randomization at Visit
- Double-blind Treatment Phase: relates to the period starting immediately after the date/time of randomization and ending the day of the EOT visit, Visit
- Post-Treatment Phase: relates to the period starting from the day after the EOT visit, Visit

If a visit is split across 2 days, completion of the full study visit is when all assessments on the 2nd day have been completed. Hence the end date of the visit should be used in phase derivations where applicable.

Definition of study day

Throughout this SAP any references to "Visit XX" refer to the pre-specified visits defined in the protocol. Data listings will additionally present study day. Study day will be calculated relative to the first date of administration of randomized study treatment (Study Day 1). There is no Study Day 0. The day before Study Day 1 is Study Day 1.

Definition of baseline and run-in baseline

Baseline is defined as the last non-missing value or mean values, where assessments are made in triplicate such as for ECGs, prior to the subject receiving randomized study treatment. Scheduled and unscheduled assessments will be considered.

Run-in baseline is defined as the last non-missing value or mean values, where assessments are made in triplicate such as for ECGs, prior to the subject receiving any study treatment, including assessments will be considered. This baseline will be used to assess the effect of the treatment taken during the run-in period for selected safety data. For ECG, where assessments are performed in triplicate more than once at a visit, the relevant time-matched baselines will be used for the analysis of data, where applicable.

Definition of End of Treatment (EOT)

End of treatment is defined as Visit (Week or the last visit in the study for subjects lost to follow-up or those who were withdrawn from the study by investigator.

• Incomplete dates

Every effort will be made to minimise incomplete dates. For calculation purposes, incomplete dates will be completed using worst case. Further details are detailed in the relevant sections as required.

Non-numeric values

In the case where a variable is recorded as ">x", " \geq x", " \leq x", or " \leq x", then for analysis purposes a value of x will be taken. Where a range of values is quoted the midpoint of the range will be taken. For example, if a laboratory safety parameter is reported as being below the limit of quantification or < x, the value of the limit will be used in the calculation of summary statistics. The recorded value will be reported in listings.

Methods for handling missing item responses in the Congenital DM1 Rating Scale (CDM1-RS)

For this measure, either clinician-completed, caregiver-completed or independent rater-completed, one or more individual items may have a missing response at a given time point while the remaining items have been completed. Without imputation this would result in a missing total score. In order to avoid this scenario, each individual missing item will be replaced by the mean of that item alone from subjects within the same treatment group at that time point. The total score will then be computed using these values. This will be done before any other missing data methods are applied.

Methods for handling withdrawals and missing data

For the primary and key secondary estimands, missing data will be accounted for using a direct likelihood approach (MMRM) and multiple imputation (MI) will be used in sensitivity analyses. MMRM models handle missing data by assuming it is missing at random (MAR), so that mean changes from baseline are estimated assuming that subjects with missing data will perform in the same way as subjects with the same covariate values and the same observed data so far. MI uses data from those subjects with similar characteristics to those with the missing data to impute a value for each subject and produces an imputed dataset. This process is repeated multiple times. For

each imputed dataset, an analysis is completed and the estimates from each analysis are combined to provide the estimates for the endpoint.

Some exploratory endpoints utilize ANCOVA models, with a subject with missing data at baseline and/or Visit being excluded from the analysis. Missing data for these models will be assumed to be missing completely at random (MCAR). Analyses will also be done to explore the effect of missing not at random (MNAR) scenarios on the results.

Prior to database lock, the data will be reviewed to assess whether any subjects were unable to complete an assessment due to "extreme" factors affecting their ability to complete an assessment e.g. due to a serious deterioration in their physical state. In the event that such subjects are identified, additional appropriate methods for handling this specific type of missing data may be used.

Further details are given in section 6.13 below.

Visit Windows

[figure not shown]
All subjects are expected to have an in-clinic visit for all pre-specified timepoints (except for the collection of AE and concomitant medication data at Visits and Should an in-clinic visit be missed a telehealth visit can replace it using the following rules:

Telehealth visits falling within and days of the expected date of a post-randomization in-clinic visit up to Visit and days of the expected date of Visits and where the expected date is calculated from the randomization visit (Visit and Law Where the expected date is calculated from the randomization visit (Visit and Law Where the expected date is calculated from the randomization visit (Visit and Law Where Law W

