11.6 Missing data

In the analysis of the primary, key secondary, and secondary endpoints, sensitivity analyses will be performed to examine the potential influence of missing data. Depending on the actual data patterns, various imputation methodologies may be employed. Multiple imputation methodology may be used with missing data imputed by randomized arm according to the within arm distribution of the observed, non-missing data. Alternatively, the mean value within treatment group at a given time point may be imputed. Full details of the approach to examine the influence of missing data will be included in the Statistical Analysis Plan. The missing data will not be imputed for mixed effects models. No imputations will be performed for per protocol analysis.

If in-clinic data are missing due to a subject's inability to attend clinic due to COVID-19 related reasons, the corresponding telehealth data can be utilized instead. If both in-clinic and telehealth data are missing, the imputations described above may be utilized.

Protocol No: AMO-02-MD-2-003

AMO Pharma Ltd.

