- Subjects who prematurely discontinue the study due to COVID-19 will be identified as described in section 6.6 and will be presented as a reason for withdrawal of 'COVID-19'.
- Missing efficacy data for the primary and key secondary estimands will be subject to the imputation and analysis methods described in sections 6.13.1 and 6.13.2.

In order to provide supportive information for interpretation of the key efficacy and safety analyses, a summary of the number and percentage of subjects with missing in-clinic (telehealth assessment only being available) and completely missing assessments (no in-clinic or telehealth assessment being available) at each scheduled visit will be presented by treatment group and overall for the following selected data on the ITT analysis set or safety analysis set (safety data) as appropriate:

- Primary and secondary efficacy endpoints (specifically in-clinic and telehealth Clinician Completed CDM1-RS, clinician in-clinic and telehealth CGI-I, Top 3 Caregiver concerns, Caregiver Completed CDM1-RS, 10-meter walk-run test)
- Clinical chemistry and complete blood counts
- ECGs

A summary of missing items for the clinician in-clinic and telehealth CDM1-RS and caregiver CDM1-RS will also be produced.

If these summaries suggest that further investigation is beneficial, additional summaries and/or analyses may be added post hoc to address missing data or assessments outside of protocol defined windows. This may include but is not limited to: additional sensitivity analyses of the efficacy endpoints, additional summaries of selected safety data for overall worst case post-baseline values, application of visit windows to group post-baseline data across multiple visits as appropriate.

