6.13.3.2 Caregiver-Completed Congenital DM1 Rating Scale (CC-CDM1-RS)

The CC-CDM1-RS is completed by the caregiver to score the symptom severity of the domains that are clinically relevant in Congenital DM1. This scale is analogous to the Clinician Completed CDM1-RS. The severity of the caregiver's concern in each domain is scored by using a 5-point Likert Scale. Scores range from 0 = Not present to 4 = Very severe. The CC-CDM1-RS is assessed at Visits and may be completed at home if required due to a COVID-19 related reason.

The CC-CDM1-RS total score will be derived at each visit as the total score based on 11 domain ratings, with a higher score indicating worse symptom severity. If one or more of the 11 items is missing then the total score will be set to missing.

An MMRM model will be fitted to the change from baseline to end of treatment in the CC-CDM1-RS in a similar manner to the primary estimand (see Section 6.13.1). The MMRM model will contain treatment, age group, visit and treatment by visit interaction as fixed effects, baseline CC-CDM1-RS as a covariate.

The CC-CDM1-RS total score and corresponding change from baseline will be summarised over time. In addition, the CC-CDM1-RS total score at Visits and the change from Visit to will be summarised.

The change from baseline in CC-CDM1-RS total score will be presented over time using by subject line plots by treatment group. In addition, line plots will present the adjusted LS mean changes from baseline and SEs over time, as estimated by the MMRM model, by treatment group.

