6.13.4.3 Congenital and Childhood Myotonic Dystrophy Health Index (CC-MDH1) Parent Proxy Instrument

The CC-MDHI Parent Proxy is a 19 category, 128-item Likert scale that covers multiple aspects of the specific phenotype of Congenital DM1, intended for completion by the caregiver of the subject. Each item offers 6 levels of severity ranging from "he/she doesn't experience this" to "it affects his/her life severely". The CC-MDHI will be administered at Visits and and Each item will be scored 0 (corresponding to "he/she doesn't experience this" to 5 (corresponding to "it affects his/her life severely").

The CC-MDHI total score will be derived at each visit as the total score based on the 128 items, and the score within each of the 19 categories will also be calculated. A higher score indicates worse symptoms or severity. If one or more items is missing, the scores will be imputed based on the values of the other items in that category in which the item is missing by taking the average of the non-missing items and multiplying by total number of items (non-missing and missing) included in the score. This will be done provided at least half of the items within a particular category are non-missing.

An ANCOVA will be fitted to the change from baseline to end of treatment in the CC-MDHI total score. The same will be done for the total scores in each of the 19 categories. The model will be fitted and results presented as described in section 6.13.4.1 for the DXA scan.

Summary statistics of observed values with corresponding change from baseline will be presented as continuous by visit and treatment. Line plots will present the adjusted LS mean changes from baseline to end of treatment and SEs, as estimated by the ANCOVA, by treatment group.

The CC-MDHI data will be listed.

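### SAP 6.3 and 6.13.3.2 give incompatible missing-item rules for the caregiver CC-CDM1-RS total, and no listed sensitivity analysis varies the 6.3 arm-mean fill that also feeds the primary CDM1-RS total

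*SAP*

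**What the plan says.** **The general rule.** SAP 6.3 has a paragraph on missing CDM1-RS items that names the clinician, caregiver and independent-rater versions. To avoid losing the total, "each individual missing item will be replaced by the mean of that item alone from subjects within the same treatment group at that time point". A total is then computed, and this step comes before every other missing-data method.

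**The caregiver rule.** SAP 6.13.3.2, on the CC-CDM1-RS, says: "If one or more of the 11 items is missing then the total score will be set to missing".

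**Precedence.** The only text that bears on it is the opening of 6.3: "Derivations specific to the parameter of interest are detailed within the specific SAP section".

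**The primary endpoint.** SAP 6.13.1 defines the CDM1-RS total as the sum of 11 ratings and gives no item rule of its own, so the 6.3 fill applies before the MMRM.

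**What is planned on missing items.** SAP 6.12 promises a description: "A summary of missing items for the clinician in-clinic and telehealth CDM1-RS and caregiver CDM1-RS will also be produced". If it suggests that more is needed, "additional summaries and/or analyses may be added post hoc to address missing data".

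**The protocol.** Section 11.6 allows an arm-mean option among its sensitivity analyses: "Alternatively, the mean value within treatment group at a given time point may be imputed". It then says that missing data are not imputed for mixed effects models, and that nothing is imputed in the per-protocol analysis. SAP 6.18, which lists changes from the protocol analysis, does not mention the item fill.

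**The concern.** Take a caregiver form with 10 of 11 items rated. SAP 6.3 gives that child a total; SAP 6.13.3.2 gives none. Two programmers working from the same SAP could build different caregiver datasets with different children in the model. The 6.3 fill also needs treatment codes, so its totals for incomplete forms cannot be produced while the data are blinded.

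On the primary endpoint the issue is different. The filled item is an average over other children in the arm. It does not use the child's own other ratings, and it enters the MMRM as if it had been observed, so its uncertainty does not reach the standard error. If many items were missing, the test would be somewhat too liberal, and no planned analysis would show it.

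**Working it through.** **1. How many forms the two caregiver rules treat differently.** The documents give no item-missing rate, so the rate q is an assumption, shown as a range. With 11 items missing independently, the share of incomplete forms is 1 − (1 − q)^11. SAP section 3 reports 53 children randomized.

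| q | incomplete forms | of 53 at one visit | totals left under 6.13.3.2 |
|---|---|---|---|
| 0.5% | 1 − 0.995^11 = 5.4% | 2.8 | 50.2 |
| 1% | 1 − 0.99^11 = 10.5% | 5.5 | 47.5 |
| 2% | 1 − 0.98^11 = 19.9% | 10.6 | 42.4 |
| 5% | 1 − 0.95^11 = 43.1% | 22.9 | 30.1 |

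Under 6.3 all 53 totals are kept. Clustering lowers these shares. At q = 1% about 0.01 × 53 × 11 = 5.8 items are missing at a visit; if all sat on one form, the rules would differ on 1 of 53 forms.

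**2. What that loss could cost.** Protocol 11.1 gives an SD of change of 2.64, a difference of 2.2 and 82% power with 25 per group. Check: 2.2 / (2.64 × √(2/25)) = 2.2 / 0.747 = 2.95, which gives 83.8% by the normal approximation and 82.3% by the noncentral t. The stated figure reproduces. The caregiver SD is not in the documents, so the primary-scale values stand in here for illustration only. A single-visit comparison has 84.5% power at 26.5 per arm. It has 80.2%, 75.5% and 59.8% at the 23.7, 21.2 and 15.1 per arm left by the 6.13.3.2 rule at q = 1%, 2% and 5%.

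**3. The fill on the primary total.** Two simulations assumed no treatment effect and items missing completely at random after baseline.

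- *MMRM:* 25 per arm, 11 integer items scored 0–4, change SD about 2.64, three post-baseline visits (assumed, because visit numbers are redacted), three inter-item correlations (0.05, 0.24, 0.52), and 10,000 trials per cell (Monte Carlo SE about 0.22 points). A t reference replaced Kenward-Roger.
- *ANCOVA at end of treatment:* 27 versus 26, continuous items, two baseline item SDs, 4,000 trials per cell with missing items (Monte Carlo SE √(0.05 × 0.95 / 4000) = 0.34 points).

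| q | type I error, MMRM | type I error, ANCOVA | model SE / true SE, MMRM |
|---|---|---|---|
| complete data | 4.7–5.2% | 5.3% | – |
| 1% | 4.8–5.6% | 5.1%, 6.1% | 0.98–0.99 |
| 2% | 5.3–6.0% | 5.4%, 5.8% | 0.97–0.98 |
| 5% | 6.3–6.7% | 6.2%, 6.7% | 0.94 |
| 10% | 8.1–9.1% | 8.2%, 8.4% | 0.86–0.89 |

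The lone 6.1% at q = 1% is above the 5.4% found at q = 2% in the same setting, and the larger simulation does not support it; it looks like noise. With a true effect of 2.14, the filled analysis estimated 2.13–2.14 at every rate, so there is no bias when items are missing completely at random. Item-level multiple imputation gave type I error of 4.6–4.8% (3,000 trials, q = 1–10%). Setting the total to missing under the MMRM gave 4.7–5.6%; its 10% setting did not fit and is not reported.

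**4. Whether a planned analysis varies the fill.** In SAP 6.13.1.1, analyses 1, 2, 7 and 8 change how missing visits are imputed. Analyses 3 and 4 change the visit mode, 5 restricts to completers and 6 changes the test. All take the total as 6.3 forms it. The responder and subgroup analyses use that same total, and the FAS repeat changes only the population. The single-item MMRMs model each item separately, so they give no standard error for the total. The PPS repeat would drop the fill if Protocol 11.6 is read literally, but it also changes the population.

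**The case against.** **Specific over general.** Section 6.3 presents general derivations and points to the specific sections, and 6.13.3.2 is the specific section for this scale. That is a natural reading. But the opening sentence of 6.3 is a signpost, not a rule of precedence, and the item paragraph below it is itself scale-specific and names the caregiver version. A reader might infer that the SAP cannot be followed at all; that goes too far. The conflict arises only for incomplete caregiver forms, on an endpoint that SAP 6.14 treats as supportive.

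**No shown harm to the primary.** This largely stands. Clinicians rate 11 items with a standard interview and examination form, and a score of 0 covers an absent symptom, so gaps may be rare. A reader might infer from the 5% and 10% rows that the primary test is inflated. The documents do not support that, because they give no missing-item rate and suggest none that high.

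**Something may vary the fill.** The single-item models and the PPS run come close, and a flat claim that nothing touches the fill would be too strong. The SAP does not say whether either uses unfilled items, and neither is a clean test of the total.

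**A route exists to settle it blind.** SAP 6.2 lets the blinded review decide on "changes required to the SAP". A reader might infer that the rule would be chosen with results in view; nothing in the documents shows that.

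**Protocol breach.** A reader might infer a plain breach of Protocol 11.6. Its sentences do conflict with filling items before an MMRM, but the section never mentions item-level gaps and leaves detail to the SAP. Reconciliation is needed; a breach is not established.

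**Conclusion.** The caregiver conflict is certain from the text and should be settled. Its size depends on an unknown rate: the rules differ on about 10%, 20% or 43% of forms at a visit if 1%, 2% or 5% of items are missing independently, and on fewer if gaps cluster. It concerns a secondary endpoint with no confirmatory decision attached.

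The point on the primary endpoint is correct in kind but conditional. The fill is a single imputation analysed as observed, and none of the eight listed sensitivity analyses varies it. Under missingness completely at random its effect is small at 1–2% of items missing, and type I error rises to about 6–7% at 5%. The unreconciled wording of Protocol 11.6, and the silence of SAP 6.18, are documentary gaps that stand whatever the rate.

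**What to change.** 1. **Caregiver total.** By SAP amendment at or before the blinded data review, state which single item rule governs the CC-CDM1-RS total, and delete the other or replace it with a cross-reference. If unblinding has passed, report which rule was used and show the other as a sensitivity analysis. The SAP Addendum of August 2024 makes this useful, since it reuses the caregiver total in a subgroup MMRM (2.5) and correlates the two scales (2.6).

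2. **Primary total.** If the 6.3 fill is kept, prespecify one sensitivity analysis. Use item-level multiple imputation conditional on the child's own items, combined by Rubin's rules, or set the total to missing and let the MMRM handle it.

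3. **Protocol.** Reconcile the fill with Protocol 11.6, say whether it applies in the PPS run, and list it in SAP 6.18.

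Optional, as a matter of preference: a minimum number of rated items, for which the SAP has a precedent in its CC-MDHI rule ("This will be done provided at least half of the items within a particular category are non-missing"), or a fill based on the child's previous rating. The threshold would rarely act if items are missing at random, and the previous-rating fill is again a single imputation, across domains that differ in kind.

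The cost is a few SAP sentences, minor programming and one extra table.

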6.4 Analysis Sets

The following analysis set definitions will be used:

The Enrolled Set includes all subjects for whom informed consent has been provided and assent provided (if applicable), irrespective of whether they received any study treatment.

The **Safety Analysis Set (SAF)** consists of all randomized subjects who received at least one dose of study treatment. Subjects will be presented by treatment actually received. The SAF is the primary population for the analysis of safety data.

The Intent-To-Treat (ITT) set consists of all randomized subjects with at least one post-baseline efficacy assessment. Subjects will be presented in the treatment group they were randomly assigned to. The ITT is the primary population for the analysis of efficacy data.

The Full Analysis Set (FAS) will include all randomised subjects in the SAF for whom any efficacy data were collected post randomisation. Subjects will be included in the analysis set according to the treatment they actually received.

The Pharmacokinetic Analysis Set (PKAS) consists of all subjects in the ITT who receive tideglusib and have at least one evaluable post-dose PK measurement (even if below the limit of quantification). Evaluable PK measurements are defined as those

with dosing information prior to sample collection and sample collection information available. Subjects will be analyzed according to the treatment actually received.

The Per-Protocol Set (PPS) will include all subjects in the FAS who did not have any important protocol violations. Definitions of important protocol violations will be included in the SAP prior to data lock and unblinding. Subjects excluded from the PPS will be determined prior to data unblinding. If no subjects are excluded from the PPS, the PPS will not be required. The PPS will be used for secondary analyses of efficacy data.

All protocol deviations will be assessed and documented on a case-by-case basis prior to the database lock. Important protocol deviations are a subset of protocol deviations that may significantly impact the completeness, accuracy, and/or reliability of the study data or that may significantly affect a subject's rights, safety, or well-being. Important protocol deviations and their impact on the analysis sets for this study are specified in the Protocol Deviations Criteria (PDC) form. Only important protocol deviations will be included in the statistical outputs.

The definitions for the Enrolled, PKAS, RIS, SAF, ITT and FAS analysis sets are sufficient to determine the subjects included within these analysis sets and so do not require listing and manual review for approval.

